5.2. Other Baseline Characteristics

Other Baseline characteristics include serum creatinine, serum cystatin C, eGFR_{cr}, eGFR_{cys}, UACR, stage of disease (defined by eGFR_{cr} and UACR), blood urea nitrogen, potassium, calcium, phosphorus, bicarbonate, fasting blood glucose, fasting blood insulin, and HbA1c. These Baseline characteristics will be summarized by randomization status, treatment group and overall using descriptive statistics (n, mean, SD, median, Q1, Q3, minimum, and maximum) for continuous variables and using number and percentage of subjects for categorical variables. The summary of these Baseline characteristics will be provided for the Safety Analysis Set. No formal statistical testing is planned.

A by-subject listing of other Baseline characteristics will be provided by subject ID number in ascending order.

5.3. Medical History

Medical history will be collected at screening for disease-specific and general conditions (i.e., conditions not specific to the disease being studied).

Disease-specific medical history will be summarized by treatment group and overall by the number and percentage of subjects with each prepopulated condition. A summary of disease-specific medical history will be provided for the Safety Analysis Set. No formal statistical testing is planned.

General medical history data will not be coded but will be listed only.

6. EFFICACY ANALYSES

6.1. Primary Endpoint

6.1.1. Definition of the Primary Endpoint

The primary efficacy endpoint of this study is eGFR_{cr} slope from treatment-specific Baselines through Week 84. The values for eGFR_{cr} will be calculated using the CKD-EPI Creatinine Equation (2009):

$$eGFR = 141 \times \min\left(\frac{S_{cr}}{\kappa}, 1\right)^\alpha \times \max\left(\frac{S_{cr}}{\kappa}, 1\right)^{-1.209} \times 0.993^{Age} \times 1.018[\text{if female}] \times 1.159[\text{if Black}]$$

S_{cr} = standardized serum creatinine (mg/dL)

κ = 0.7 (females) or 0.9 (males)

α = -0.329 (females) or -0.411 (males)

min indicates the minimum of S_{cr}/κ or 1

max indicates the maximum of S_{cr}/κ or 1

age in years

6.1.2. Statistical Hypothesis of the Primary Endpoint

The primary analysis will test the following null hypothesis (H_0) that there is no difference in eGFR_{cr} slope from treatment-specific Baselines between SEL and placebo versus the alternative hypothesis (H_1) that eGFR_{cr} slope in the SEL arm is larger than that in the placebo arm.

Formally,

$$H_0: \beta_{SEL} = \beta_{PBO} \text{ vs. } H_1: \beta_{SEL} > \beta_{PBO}$$

where β_{SEL} and β_{PBO} denote the mean slope from treatment-specific Baselines for SEL and placebo, respectively.

Statistical testing will be conducted at a 1-sided Type 1 error level of 0.15.

6.1.3. Analysis of the Primary Endpoint

The Primary Analysis Set for efficacy analyses is the Full Analysis Set.

Definition of Baseline

Baseline eGFR_{cr} for the primary analysis is defined as below:

- SEL arm: The average of the measurements at Visit C and Visit 1. This Baseline will also be referred to as post-run-in Baseline.

- Placebo arm: The average of the measurements at Visit A (enrollment) and Visit B. This Baseline will also be referred to as pre-run-in Baseline.

Estimand

The Treatment Policy estimand is defined as follows. This is the primary estimand for the primary endpoint.

- 1) Population: Subjects in the FAS. See definition of the FAS in Section 3.1.3.
- 2) Variable: Primary endpoint (eGFR_{cr} slope from treatment-specific Baselines through Week 84). See Section 6.1.1 for detailed definition of the primary endpoint.
- 3) Intercurrent events: Intercurrent events for this study include study treatment discontinuation and/or starting a concomitant medication (e.g. SGLT-2 inhibitors).

The occurrence of an intercurrent event is irrelevant. All observed values will be used regardless of occurrence of an intercurrent event.

- All observed values will be used regardless of occurrence of an intercurrent event (i.e, All available data defined above)
 - If a subject is lost to follow up, treat data as missing from the point of loss to follow-up onward
- 4) Population-level summary: eGFR_{cr} slope from treatment-specific Baselines through Week 84 in each treatment arm, and difference in eGFR_{cr} slope from treatment-specific Baselines through Week 84 between SEL and placebo treatment arms.

Main Estimator

A random slope model will be used to evaluate SEL treatment effect on eGFR_{cr} slope from treatment-specific Baselines through Week 84. The random slope model will have eGFR_{cr} change from treatment-specific Baselines at Weeks 4, 8, 12, 24, 36, 48, 60, 72 and 84 as outcome, and will include terms for eGFR_{cr} at treatment-specific Baselines as a continuous variable, pre-run-in Baseline UACR category (< 1500 mg/g vs. ≥ 1500 mg/g), concomitant use of SGLT-2 inhibitors at Randomization, treatment group, week, and treatment-by-week interaction. Within-subject variance covariance will be modeled as unstructured. If model convergence problems arise, other variance-covariance structures, such as Heterogeneous Toeplitz, will be considered and documented.

Sensitivity analyses of the eGFR_{cr} slope endpoint will include the following:

- Sensitivity analysis of eGFR_{cr} slope excluding off-treatment eGFR_{cr} values from the SEL treatment group.

- Sensitivity analysis of eGFR_{cr} slope excluding eGFR_{cr} values collected after the initiation of dialysis or kidney transplantation.
- Sensitivity analysis to evaluate the impact of attenuation of the acute effect. For subjects in the SEL group, the on-treatment eGFR_{cr} values will be adjusted using a regression model as described in [Appendix 2](#), which takes into account attenuation of the acute treatment effect that may be due to the theoretical concern for loss of kidney function over time. For subjects in the placebo group, the observed eGFR_{cr} values will be used. The analysis of eGFR_{cr} slope will be performed using the same model as described in the primary analysis, except that pre-run-in Baseline eGFR_{cr} will be used for both SEL and placebo arms.
- Sensitivity analysis of eGFR_{cr} slope in subjects who completed study treatment.
- Sensitivity analysis of eGFR_{cr} slope excluding subjects with randomization stratification mismatch between IXRS and Clinical Database.
- Sensitivity analysis of eGFR_{cr} slope excluding subjects who took prohibited medications that may affect SEL efficacy or decrease SEL drug level in the prohibited period as detailed in [Appendix 3](#).
- Sensitivity analysis of eGFR_{cr} slope from pre-run-in Baseline for both SEL and placebo arms.
- Sensitivity analysis of eGFR_{cr} slope from treatment-specific Baselines through Week 48.
- Sensitivity analysis of eGFR_{cr} slope from treatment-specific Baselines through Week 60.
- Sensitivity analysis of eGFR_{cr} slope from treatment-specific Baselines through Week 72.
- Sensitivity analysis of eGFR_{cr} slope from treatment-specific Baselines through Week 96.

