1.2.3. Clinical Trials of Selonsertib

As of 17 July 2019, 10 Phase 1, 6 Phase 2, and 3 Phase 3 clinical studies have been conducted/are ongoing in which 390 healthy subjects, 248 subjects with DKD, an estimated 40 subjects with CKD, 1473 subjects with NASH, 50 subjects with AH, and 145 subjects with PAH have been dosed with SEL. Across these studies, SEL was generally well tolerated. No adverse drug reactions with SEL have been identified to date.

Information on the completed and ongoing clinical studies can be found in the IB. Brief summaries of an additional Phase 1b study and the completed Phase 2 study relevant to this protocol are provided below.

1.2.3.1. A Phase 1b, Randomized, Blinded, Placebo-Controlled Study to Evaluate the Effect of Selonsertib on Renal Function as Assessed by Markers of Glomerular Filtration Rate in Subjects with Chronic Kidney Disease (GS-US-223-0110)

Study GS-US-223-0110 is a Phase 1b, blinded, randomized, placebo-controlled study that evaluated the effect of SEL on kidney function in subjects with CKD using markers of estimated (eGFR_{cr}) and measured GFR (mGFR, as assessed by iohexol clearance). Subjects (n = 82) with CKD (eGFR_{cr} 20 to < 60 mL/min/1.73 m²) were randomized 1:1 to receive SEL 18 mg or placebo once daily for 28 days followed by a 28-day washout period. After adjusting for baseline

eGFR_{cr} and placebo treatment, a 4.8% decrease in mGFR on Day 7 and a decrease of 5.7% (approximately 2 mL/min/1.73 m²) on Day 28 in the SEL treatment group was observed. This acute decrease in mGFR was reversible and deemed not clinically significant, as evidenced by no decrease in the SEL treatment group relative to placebo on Day 56. Compared with mGFR changes, there was a slightly larger decrease in eGFR_{cr} in the SEL treatment group relative to placebo on Days 7 and 28 (7.0% and 6.5%, respectively) that was reversible on Day 56. Study conduct is currently complete and writing of the clinical study report is ongoing.

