1.2.3.2.2. Subject Disposition

Of the 334 randomized subjects, 333 subjects received at least 1 dose of study drug: 85 subjects received placebo and 248 subjects received SEL (81, 84, and 83 subjects received SEL 2, 6, and 18 mg, respectively).

A total of 256 subjects (76.9%) completed treatment and 76 subjects (22.8%) discontinued study drug (19 subjects [22.4%] in the placebo group and 57 subjects [23.0%] in the pooled SEL group [18.5%, 21.4%, and 28.9% for SEL 2, 6, and 18 mg, respectively]). The most frequent reason for discontinuation of study drug was due to an adverse event ([AE], 4 subjects [4.7%] in the placebo group and 18 subjects [7.3%] in the pooled SEL group), followed by progression to end stage kidney disease (ESKD) (4 subjects [4.7%] in the placebo group and 13 subjects [5.2%] in the pooled SEL group), and withdrawal of consent (3 subjects [3.5%] in the placebo group and 13 subjects [5.2%] in the pooled SEL group).

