Due to this acute (potentially artefactual) effect observed in prior studies, this Phase 2b study has incorporated a Run-in design to account for the acute eGFR effect in order to better characterize the chronic (long-term) effect of SEL on eGFR. To maintain the integrity of the study, other than eGFR values < 15 mL/min/1.73 m², eGFR results collected at Visits A, B, C, and Visit 1 will not be released to subjects, investigators or sponsor before study unblinding. All eGFR values starting at week four will be released to subjects, investigators and the sponsor for safety monitoring and treatment decisions.

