3.4. Discontinuation of Study Drug

Selonsertib or PTM should be discontinued for any of the following reasons in consultation with the Gilead Medical Monitor and/or sponsor designee:

- Death
- Kidney failure (dialysis performed for at least 4 weeks, kidney transplantation, or confirmed decrease in eGFR to $< 15 \text{ mL/min/1.73 m}^2$ for subjects without dialysis or kidney transplantation)
- Pregnancy during the study; refer to [Appendix 6](#)
- Participation in another therapeutic clinical study
- Clinically significant adverse event in the opinion of the subject or investigator
- Significant protocol violation that impacts subject safety
- Significant subject noncompliance with study drug administration, study procedures, or study requirements per judgement of the investigator
- Intercurrent illness that would, in the judgment of the investigator, *permanently* affect assessments of clinical status to a significant degree
- Unacceptable toxicity, or toxicity that, in the judgment of the investigator, compromises the ability to continue study-specific procedures or is considered to not be in the subject's best interest
- Study blinding is intentionally broken by the subject or the study site
- Discontinuation of the study at the request of Gilead, a regulatory agency, or an institutional review board or independent ethics committee (IRB/IEC)

Subjects who permanently discontinue study drug will have an end of treatment (EOT) visit scheduled as soon as possible after the decision to discontinue study drug is made. If an ECG, STS was conducted at a previous visit within 24 weeks of the EOT visit, the assessment does not need to be performed at the EOT visit. In addition to the EOT visit, subjects who permanently discontinue study drug prior to global study end date will have a 30 day (± 7 days) EOT Follow-up visit which will include an assessment of eGFR and UACR.

Every attempt should be made to keep these subjects in the study and complete all subsequent study visits in the same way as subjects who are still on study drug. If this is not possible, subjects off study drug will have the option to be followed via limited assessments as defined in Section 6.7.2.

Subjects who have permanently discontinued study drug, reached kidney failure, or are no longer able to continue to attend clinic visits in-person, and have not withdrawn full consent will be asked to continue to participate in this study via remote assessments as defined in Section 6.7.3.

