4.4. Eligibility Criteria for Randomization

Subjects must meet *all* of the following criteria to be eligible for randomization:

- 1) eGFR \geq 15 mL/min/1.73 m² at all central laboratory assessments during the Run-in period prior to Randomization (Visit 1)
- 2) At least 7 consecutive daily doses of SEL, without interruption, immediately prior to Visit C and prior to Randomization (Visit 1)
- 3) Subject did not permanently discontinue study drug during the Run-in period
- 4) Subject did not withdraw consent
- 5) Subject did not initiate, change dose, or discontinue SGLT-2 inhibitor during the Run-in period or is not anticipated to initiate, change dose or discontinue SGLT-2 inhibitor within 12 weeks after Randomization (Visit 1)
- 6) Negative urine pregnancy test for female subjects of childbearing potential
- 7) No ongoing clinically significant illness, medical condition, surgical history, physical finding, or laboratory abnormality that, in the investigator's opinion, could adversely affect the safety of the subject or impair the assessment of study results

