8.5.1.1. Analysis of eGFR Slope

Definition of Baseline

Baseline eGFR_{cr} for the primary analysis is defined as below:

- SEL arm (Arm A): The average of the measurements at Visit C and Visit 1. This baseline will also be referred to as post-run-in baseline.
- Placebo arm (Arm B): The average of the measurements at Visit A (enrollment) and Visit B. This baseline will also be referred to as pre-run-in baseline.

The primary analysis of eGFR_{cr} slope will be performed after all subjects in the ITT Analysis Set complete the Week 48 visit or discontinue from the study. Pre-run-in baseline eGFR_{cr} and post-run-in baseline eGFR_{cr} will be used for the placebo and SEL arms, respectively. Baseline eGFR_{cr} as well as all on- and off-treatment eGFR_{cr} values collected after Visit 1 through time of the analysis for all subjects with available data will be included. eGFR_{cr} slope will be compared between SEL and placebo using a random slope model. The random slope model will have eGFR_{cr} values starting from Baseline as the outcome, and will include terms for pre-run-in baseline eGFR_{cr} as a continuous variable, pre-run-in baseline UACR category (< 1500 mg/g vs. ≥ 1500 mg/g), concomitant use of SGLT-2 inhibitors, treatment group, visit, and treatment-by-visit interaction. The difference in eGFR_{cr} slope between SEL and placebo groups will be estimated and tested.

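### The primary slope keeps eGFR values taken after SEL is stopped, so reversal of SEL's acute dip can be read in part as slower decline, and the planned check for this covers the SEL arm only

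*SAP*

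**What the plan says.** - **Estimand.** SAP 6.1.3 declares a treatment-policy estimand and names treatment discontinuation as an intercurrent event: "All observed values will be used regardless of occurrence of an intercurrent event". Protocol 8.5.1.1 likewise includes "all on- and off-treatment eGFR_{cr} values collected after Visit 1 through time of the analysis".
- **Baselines (SAP 6.1.3).** SEL uses the mean of Visit C and Visit 1, taken on SEL. Placebo uses the mean of Visits A and B, taken before SEL.
- **Model (SAP 6.1.3).** A random slope model for change from baseline at Weeks 4 to 84, with treatment, week and treatment-by-week terms.
- **Test (SAP 6.1.2).** "Statistical testing will be conducted at a 1-sided Type 1 error level of 0.15".
- **Purpose of the run-in (Protocol 1.3).** The study uses "a Run-in design to account for the acute eGFR effect" so that the chronic effect can be characterised better.
- **The dip (Protocol 1.2.3.1).** The placebo-adjusted falls in eGFRcr at Days 7 and 28 are given as "7.0% and 6.5%, respectively) that was reversible on Day 56", after a 28-day washout.
- **Off-drug data.** Permanent stoppers have a 30-day "EOT Follow-up visit which will include an assessment of eGFR and UACR" (Protocol 3.4) and are asked to attend all later visits (6.7). After kidney failure, clinic eGFR ends with the 30-day visit (6.5). Remote follow-up has no clinic visits (6.7.3).
- **Sensitivity analyses (SAP 6.1.3).** These include excluding off-treatment values from the SEL group, using the pre-run-in baseline in both arms, restricting to treatment completers, and the Appendix 2 adjustment.

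**The concern.** A SEL subject who stops and is still measured loses the dip, so eGFR steps up for a reason unrelated to preserved kidney function. A placebo stopper has no such step. A straight-line treatment-by-week term has no place for a step and absorbs part of it as a shallower SEL slope. That lets back into the primary result the acute effect that the run-in was meant to separate out. At stake is whether a positive primary test can be read as slowing of chronic decline, and whether the listed sensitivity analyses would show it if it cannot.

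**Working it through.** **1. The plan's own figure.** The standard error is 10 x sqrt(2/150) = 1.155 and the one-sided 0.15 critical value is 1.036. Power for 3.7 is Phi(3.7/1.155 - 1.036) = 98.5% with 150 per arm, and 97.2% with 127. The stated 99% and 97% are reproduced. The smallest significant difference is 1.036 x 1.155 = 1.20.

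**2. Size by hand.** Assume no chronic effect, exponential stopping, full reversal and every stopper measured. The mean SEL curve then rises by dip x F(t), where F(t) is the share stopped by week t. From Week 4 to Week 84 (80/52 = 1.54 years) the spurious slope is about dip x [F(84) - F(4)] / 1.54.
- The dip in mL/min/1.73 m2 needs a baseline, which is assumed to be 35 (Protocol 1.2.3.1 equates 5.7% with about 2, and 2/0.057 = 35). A dip of 5.7% is then 2.0 and one of 6.5% is 2.3. The 5.7% is the measured-GFR fall and serves only as a lower assumed value. The eGFRcr fall at Day 28 was 6.5%.
- 15% stopped by Week 48: the weekly hazard is -ln(0.85)/48 = 0.00339, F(84) = 0.248 and F(4) = 0.013. For a dip of 2.0 the slope is 2.0 x 0.234/1.54 = 0.30.
- 28.9% stopped: the hazard is 0.00711, F(84) = 0.449 and F(4) = 0.028. For a dip of 2.0 the slope is 2.0 x 0.421/1.54 = 0.55.

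Expected generalised least squares for the random slope model gives 0.30 and 0.56. Over dips of 2 to 4, stopping of 15% or 28.9% in both arms, and half or all stoppers measured, it gives +0.16 to +1.11. At the planned standard error, rejection is 1 - Phi(1.036 - bias/1.155), or 19% to 47%.

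**3. Null simulation closer to the trial.** This used 150 per arm, follow-up of 48 to 84 weeks, the SAP visit windows, linear reversal over 28 days, 10% other dropout per 48 weeks and stopping unrelated to decline. Monte Carlo error is about 1 point.

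| Dip | Stop per 48 weeks, SEL / placebo | Stoppers measured | Bias per year | Rejects |
|---|---|---|---|---|
| 5.7% | 15 / 15% | a quarter | +0.04 | 14% |
| 5.7% | 15 / 15% | half | +0.13 | 18% |
| 5.7% | 15 / 15% | all | +0.25 | 21% |
| 6.5% | 22.4 / 22.4% | half | +0.24 | 20% |
| 6.5% | 28.9 / 22.4% | half | +0.36 | 23% |
| 6.5% | 28.9 / 22.4% | half; only the 30-day value after kidney failure | +0.41 | 25% |
| 6.5%, half reverses | 28.9 / 22.4% | half | +0.19 | 19% |
| none (control) | | | 0.00 | 15% |

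The stopping rates are from the Phase 2 study (Protocol 1.2.3.2.2): 22.4% on placebo and "18.5%, 21.4%, and 28.9% for SEL 2, 6, and 18 mg, respectively".

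**4. Would the listed checks show it?**
- *Pre-run-in baseline in both arms.* The outcome is eGFR minus baseline, from Week 4. Changing a SEL subject's baseline moves all of that subject's outcomes by one constant. This goes to the intercept and leaves the slope alone. In simulation the result stayed within 0.02 of the primary, so agreement between the two says nothing about this bias.
- *Exclusion from SEL only.* It removes the step. However, if faster decliners stop more often (hazard x1.65 per slope SD), it drops their late values from one arm. The bias was +0.21 to +0.58, with 20-29% rejection (28% even with no dip). A separate set of runs with equal stopping rates and no dip gave +0.27 to +0.73 and 20-35%.
- *The same exclusion in both arms.* With uninformative stopping: -0.08 to 0.00, 13-15%. With informative stopping at equal rates: near zero, 13-17%. With informative stopping that is also more frequent on SEL: about +0.14 to +0.24, 19-20%.
- *Completers only.* It removes the step in both arms but conditions on completing treatment. Bias was about +0.36 when stopping was informative and more frequent on SEL.
- *Appendix 2 adjustment.* In a rough run (400 null trials, known variances, upper case) it left +0.27 where the primary gave +0.41.

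**5. With a real effect.** Suppose a true on-drug effect of 3.7 is lost at stopping, 28.9% stop and all are measured. The all-values estimate is 2.76 with no rebound, 3.32 with a dip of 2.0 and 3.74 with a dip of 3.5.

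**The case against.** Treatment policy is a legitimate estimand, declared in the SAP and matched in Protocol 8.5.1.1. The null in SAP 6.1.2 is equality of slopes from treatment-specific baselines. A reader might infer from the table that the trial does not deliver its stated 0.15 level. The documents do not support that: the level is exceeded only against a null of no chronic effect, which is not the declared one. What stands is that this estimand fits poorly with the purpose of the run-in.

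A reader might also infer that the plan has no both-arm safeguard. It has one, the completer analysis, though that is biased when stopping is informative and unequal.

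Nor does the rebound always inflate the estimate beyond the true effect. With a real on-drug effect it partly offsets what is lost at stopping, as 3.32 against 3.7 shows.

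The size is also open to challenge. Dip, stopping rate and share of stoppers measured are unknown for this trial. The 28.9% comes from a study without a run-in on SEL that also enrolled subjects with eGFR below 20. Here, randomisation requires "Subject did not permanently discontinue study drug during the Run-in period", so stopping may be rarer. Remote follow-up may leave few stoppers measured. Reversal was shown only after 28 days of dosing. All of this stands, so the rejection rates must be quoted as conditional.

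**Conclusion.** The concern holds in a limited form. The mechanism follows from the documents: the SEL baseline is taken on drug, the dip reverses off drug, and off-drug values are collected and kept. If there is no chronic effect, the apparent benefit is about +0.13 to +0.41 mL/min/1.73 m2/year with half of stoppers measured. That is 4% to 11% of the planned 3.7 (0.13/3.7 and 0.41/3.7), with 18-25% rejection at a nominal 15%. It is larger if all stoppers are measured and negligible if a quarter are. These sizes rest on assumed dip, stopping, follow-up and variance inputs.

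The clearest defect is in the checks. The one aimed at off-treatment values is asymmetric and can itself favour SEL. The pre-run-in-baseline analysis cannot detect the problem under the SAP model. A reader might go further and conclude that the primary estimand is wrong and must be replaced. The documents do not compel that: it is a trade-off between estimands, and replacing it would depart from Protocol 8.5.1.1.

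**What to change.** In SAP 6.1.3:
1. Apply the off-treatment exclusion to both arms, with off-treatment defined as at least 7 days after the last dose (the interval in Appendix 2).
2. Name it the key supportive analysis, report it beside the primary result, and state that a positive primary result will be read as slowing of chronic decline only if this analysis agrees.
3. State that the pre-run-in-baseline sensitivity analysis does not address this bias.

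The cost is SAP wording and one off-treatment flag, with no new data. The downside is that the exclusion targets an on-treatment effect and assumes that stopping is ignorable given observed eGFR. It also keeps the residual bias shown in step 4 when stopping is both informative and more frequent on SEL.

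Changing the primary estimand, or formally requiring both analyses to meet 0.15, is an option for the sponsor and would need reconciling with Protocol 8.5.1.1. In simulation, requiring both rejected 12-14% under the null when stopping was unrelated to decline. It rejected 18%, against 26% for the current plan, when faster decliners stopped more often and more subjects stopped on SEL. Power at 3.7 was 97.7% against 98.7% (upper case, effect only while on drug).

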8.9. Sample Size

8.9.1. Sample Size Determination

With a sample size of 300 subjects (150 per treatment arm), power to detect a difference in $eGFR_{cr}$ decline rate of 3.7 mL/min/1.73 m²/year (common SD = 10 mL/min/1.73 m²/year) between SEL 18 mg and placebo using a two-sample t-test is 99% at a 1-sided significance level of 0.15. Assuming 15% dropout, with a sample size of 254 (127 per arm), the power is 97%.

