1.3. Sample Size and Power

With a sample size of 300 subjects (150 per treatment arm), power to detect a difference in $eGFR_{cr}$ decline rate of 3.7 mL/min/1.73 m^2 /year (common SD = 10 mL/min/1.73 m^2 /year) between SEL 18 mg and placebo using a two-sample t-test is 99% at a 1-sided significance level of 0.15. Assuming 15% dropout, with a sample size of 254 (127 per arm), the power is 97%.

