3.3. Strata and Covariates

Subjects will be randomly assigned to treatment groups via the interactive voice or web response system (IXRS) in a 1:1 ratio using a stratified randomization schedule. Stratification will be based on the following variables:

- eGFR_{cr} Strata:

eGFR _{cr} (mL/min/1.73 m ²)
≥ 45
≥ 30 to < 45
≥ 15 to < 30

- Albuminuria Strata: UACR < 1500 mg/g vs. ≥ 1500 mg/g
- Concomitant SGLT-2 Inhibitor Use Strata: Yes vs. No

Randomization will be stratified by the average eGFR_{cr} values from Visit A and Visit B; the average values of UACR from Visit A and Visit B; and concomitant use of SGLT-2 inhibitors assessed at Visit 1. Visit A and B values for eGFR_{cr} and Albuminuria will be transferred directly from the central laboratory to the IXRS for stratification but eGFR_{cr} values will not be released to sites, investigators, or the sponsor.

If there are discrepancies in stratification factor values between the IXRS and the clinical database, the values recorded in the clinical database will be used for analyses. Additionally, stratification discrepancies will be reviewed and assessed. Based on the assessment of stratification discrepancies, a sensitivity analysis of the primary endpoint may be performed.

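### The primary slope model has no stratum-by-week terms, so if the strata predict eGFR slope it takes no credit for the stratified randomization

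*SAP*

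**What the plan says.** SAP 3.3 states "Stratification will be based on the following variables" and lists three: eGFRcr in three bands, UACR below or at least 1500 mg/g, and SGLT-2 inhibitor use. The eGFR and UACR values are Visit A and Visit B averages, so they are pre-run-in values.

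The primary model in SAP 6.1.3 takes change in eGFRcr from the treatment-specific baseline at Weeks 4 to 84 as the outcome. Its terms are eGFRcr at the treatment-specific baseline (continuous), pre-run-in UACR category, and "concomitant use of SGLT-2 inhibitors at Randomization, treatment group, week, and treatment-by-week interaction". The test concerns the slope difference, and SAP 6.1.2 says "Statistical testing will be conducted at a 1-sided Type 1 error level of 0.15".

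SAP 6.2.2.3 gives the eGFRcys slope model the same structure, with pre-run-in eGFRcys as the covariate in both arms. Protocol 8.5.1.1 also stops at "treatment group, visit, and treatment-by-visit interaction", but its eGFR covariate is the pre-run-in value in both arms.

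The kidney-event analyses do use the strata: CMH in SAP 6.2.2.1, stratified log-rank and Cox in SAP 6.2.2.2. None of the slope sensitivity analyses in SAP 6.1.3 adds a stratum-by-week term.

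**The concern.** The tested parameter is a rate of change. A covariate that is constant over time and enters only as a main effect moves a subject's curve up or down and leaves its rate alone. If slope differs by UACR category, SGLT-2 use or starting eGFR, that variation stays in the random-slope variance and enlarges the standard error. Stratified randomization has meanwhile balanced those factors between the arms, so they contribute little to the real sampling variation of the slope difference. The model-based standard error then exceeds the true one, the interval is too wide, and the stratification contributes nothing to the primary slope analysis.

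The eGFR factor is in a different position from the other two. The SAP covariate is measured on SEL in one arm and before SEL in the other, and protocol 1.2.3.2.3 reports an acute fall of about 10% on 18 mg. It is not the variable used to stratify, and it could not safely be given a week interaction as it stands.

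**Working it through.** **1. The plan's own power.** The inputs are those of SAP 1.3 and Protocol 8.9.1: difference 3.7 and SD 10 mL/min/1.73 m²/year, 150 or 127 per arm, one-sided 0.15 (z = 1.036). Power = Φ(3.7 / (10·√(2/n)) − 1.036).
- n = 150: Φ(3.204 − 1.036) = 98.5%, against 99% stated.
- n = 127: Φ(2.948 − 1.036) = 97.2%, against 97% stated.

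The stated figures are reproduced to within about half a point. They come from an unadjusted comparison ("using a two-sample t-test is 99% at a 1-sided significance level of 0.15"), so they take no credit for stratification.

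**2. A main effect does not move the slope.** With complete data on a common visit schedule, a term constant over time leaves the estimated treatment-by-week effect unchanged. A generalized least squares fit to simulated complete data gave the same slope difference, 0.2613, with and without a stratum main effect. With dropout the result is approximate.

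**3. Size of the excess.** Let R² be the share of true between-subject slope variance explained by the strata. The documents do not give it; 5-20% is assumed. The variance of an estimated slope also contains measurement error, which the strata do not explain. With assumed slope SD 6 and residual SD 3.5 (also not in the documents), and weeks divided by 52:
- Visits to Week 84: Sxx = 6784/52² = 2.509. Error variance 12.25/2.509 = 4.88. Share that is true slope variance 36/40.88 = 88%.
- Visits to Week 48: Sxx = 1496/52² = 0.553. Error variance 12.25/0.553 = 22.1. Share 36/58.1 = 62%.

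With r = share × R², the SE excess is 1/√(1−r) − 1, and the actual error is 1 − Φ(1.036/√(1−r)).

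| R² | SE excess, Week 84 | Actual error | SE excess, Week 48 | Actual error |
|---|---|---|---|---|
| 0 | 0 | 0.150 | 0 | 0.150 |
| 0.05 | 2.3% | 0.145 | 1.6% | 0.146 |
| 0.10 | 4.7% | 0.139 | 3.2% | 0.142 |
| 0.20 | 10.2% | 0.127 | 6.8% | 0.134 |

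The ceiling, with no measurement error (r = R²), is an excess of 2.6%, 5.4% and 11.8%, and an error of 0.144, 0.137 and 0.123.

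**4. Simulation.** 300 subjects, 12 strata, permuted blocks of 4, complete per-subject slopes, 8,000 replicates, Monte Carlo SE 0.004. At r = 0.05, 0.10 and 0.20 the unadjusted test rejected under the null in 0.140, 0.138 and 0.125. With stratum adjustment of the slopes the figures were 0.148, 0.153 and 0.152. A full mixed-model run with dropout had only about 100 replicates per setting, too few to compare rejection rates. At R² = 0.10 its mean model SE fell from 1.23 to 1.17 with the by-week terms, in line with the formula.

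**5. Power gained.** Hold the SD of estimated slopes at 10 and let r be the share of that variance explained by the strata. Write θ for the difference divided by 10·√(2/n). As planned, power is Φ((θ − 1.036)/√(1−r)); with by-week terms it is Φ(θ/√(1−r) − 1.036).
- Difference 3.7, 150 per arm: 98.9% against 99.0% at r = 0.10; 99.2% against 99.5% at 0.20.
- Difference 3.7, 127 per arm: 97.8% against 98.1%; 98.4% against 98.8%.
- Difference 1.5, 150 per arm (θ = 1.299): 60.9% against 63.0%; 61.5% against 66.1%.

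A difference of 1.5 is illustrative. It lies inside the 95% interval of 0.25 to 7.16 around the post hoc estimate of 3.70 in protocol Table 1-2.

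**The case against.** The best defence is that nothing here threatens validity. A type I error slightly below 0.15 is harmless in a Phase 2b trial, the protocol model has the same structure, and SAP 3.4 already plans subgroup analyses of the primary endpoint by eGFR stratum, UACR and SGLT-2 use, so any dependence of slope on strata will be seen. All of that stands, and it is why the point is minor. It does not answer the efficiency point: subgroup tables do not narrow the primary interval, and the kidney-event analyses already use the strata.

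Three stronger readings are tempting, and the documents do not support them.
- A reader might infer that the 0.15 test is conservative. That holds only if the strata predict slope, and only for the effect of stratification. SAP 6.1.3 itself raises attenuation of the acute SEL effect over time, which could favour SEL on slope and push the error the other way. The net size cannot be computed from the documents.
- A reader might infer that planned power is lost. It is not, because the stated power assumes an unadjusted t-test.
- A reader might infer that all three stratification factors are in the SAP model as main effects. Only UACR category and SGLT-2 use are.

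**Conclusion.** The point holds as a minor one. Neither slope model lets a stratification factor act on the slope, and the pre-run-in eGFR stratum is absent from the primary SAP model. If the strata explain 5-20% of true slope variance, the slope SE is about 2-10% too large with visits to Week 84 (2-7% to Week 48), and the actual one-sided error is about 0.145-0.127 (0.146-0.134). If they explain none, the test is exact. These figures rest on assumed values of R², slope SD and residual SD, and they concern stratification alone. The benefit of adjusting is at most about half a point of power at the design effect, and about two to five points at a true difference of 1.5 if the strata explain 10-20% of the variance of estimated slopes.

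**What to change.** In SAP 6.1.3, replace the treatment-specific eGFR covariate with pre-run-in eGFRcr in both arms, as Protocol 8.5.1.1 does. Then add centred pre-run-in-eGFR-by-week, UACR-category-by-week and SGLT-2-use-by-week terms. The covariate must be replaced before it is given a week interaction. In SAP 6.2.2.3, where the covariate is already pre-run-in eGFRcys, add the corresponding by-week terms. Keep treatment-by-week as the test in both models.

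The cost is one changed covariate in the primary model and three extra parameters in each model, with no new data and essentially no loss of degrees of freedom at about 300 subjects. The change should be made before unblinding. If the sponsor prefers to leave the main estimator alone, the adjusted model can be listed as a sensitivity analysis, though the primary interval would then gain nothing.
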